3.2. Exclusion Criteria

- 3.2.1. Patients receiving any other investigational agents
- 3.2.2. Patients who are pregnant or breast-feeding
- 3.2.3. Patients with clinically significant heart disease (NYHA Class III or IV)
- 3.2.4. Known or suspected hypersensitivity to azacitidine or mannitol.
- 3.2.5. Patients with advanced malignant hepatic tumors.

4. Treatment Plan

4.1. **TKI:** Patients will continue receiving TKI at the dose they had been receiving during the last 6 months.

4.2. **AZA:**

Phase I: patients will be treated in cohorts of 3. The starting dose will be dose level 0 (50 mg/m²/d x 3 days subcutaneous or intravenous; Table 1).

4.2.1. At least 3 patients will be entered at each level. All patients treated at any one dose level must have been observed for at least four weeks before escalating to the next dose level. Patients who come off study prior to the first four weeks and have not experienced a DLT will be replaced.

Table 1: Dose escalation levels	
Dose level	AZA (mg/m ² /d x 3 days)
-3	25 (1 day only)
-2	25 (2 days only)
-1	25
0	50
1 (Target dose)	75
2	75 (for 5 days)
3	75 (for 7 days)

4.2.2. Dose escalation will be done as follows:

Dose-limiting toxicity in	Result
0/3	Escalate to next level
1/3	Enter 3 more patients
≥2/3 or ≥ 2/6	MTD exceeded. This dose level will be declared the maximally administered dose. Expand previous level to include a total of 6 patients if not already accrued to this number.

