1. OBJECTIVES

1.1. Primary Objective:

- 1.1.1. **Phase I:** To determine the DLT and MTD of the combination of azacitidine (AZA) and a tyrosine kinase inhibitor (TKI) in patients with chronic myeloid leukemia (CML).
- 1.1.2. **Phase II:** To determine the clinical activity of the combination of AZA and a TKI in patients with CML in complete cytogenetic remission (CCyR) with minimal residual disease.

1.2. Secondary Objectives:

- 1.2.1. **Phase I**
 - 1.2.1.1. To determine the clinical activity of the combination of AZA and a TKI in patients with CML
- 1.2.2. **Phase II**
 - 1.2.2.1. To determine the safety of the combination of AZA and a TKI in patients with CML in CCyR with minimal residual disease.
- 1.2.3. **Both phases**
 - 1.2.3.1. Determine the effect of therapy over DNA methylation
 - 1.2.3.2. Investigate the correlation of DNA methylation and response to therapy

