4.2.3. Definition of Dose-Limiting Toxicity (DLT)

4.2.3.1. DLT will be defined by events that are clinically significant and possibly related to study drug occurring during the first 4 weeks (1 cycle) of therapy.

4.2.3.2. Non-hematologic DLT is defined as grade 3 or 4 toxicity (NCI common criteria, version 4.0) that is clinically significant and

considered to be at least possibly related to the study drug. Grade 3 or 4 nausea, vomiting and diarrhea will be considered DLT only if not controlled by optimal therapy.

4.2.3.3. Grade 3 biochemical abnormalities (e.g., lipase or bilirubin elevation) will only be considered DLT if accompanied by clinical consequences. Grade 3 or 4 electrolyte abnormalities will only be considered DLT if possibly related to study drug and not corrected by optimal replacement therapy.

4.2.3.4. Hematologic DLT is defined as grade ≥ 3 neutropenia and/or thrombocytopenia with a hypocellular bone marrow lasting for 6 weeks or more after the start of a course. (In case of a normocellular bone marrow, 8 weeks with pancytopenia will be considered DLT). Anemia will not be considered for the definition of DLT.

4.2.4. If dose-level 0 exceeds MTD, subsequent patients will be treated at dose level -1. Additional cohorts at lower doses (down to dose level -4) may be included if higher doses exceed MTD. If dose level -4 exceeds MTD, the study will be terminated.

4.3. **Phase II:** The dose to be used for the phase II portion of the study is $75\text{mg}/\text{m}^2$ daily for 3 days, unless MTD is defined at a lower dose level in the phase I portion of the study in which case that would become the dose to be used for the phase II portion. Other dose levels shown in Table 1 will be used for dose adjustments for toxicity or lack of improvement (as described in section 4.5.5) during therapy. For phase II portion of the study, if at any time patients need to be escalated to dose level +2 or +3, if at any time 33% or more of patients experience DLT at this dose level during the first cycle they receive at this dose, this would be considered to have exceeded MTD and that dose level should not be used any further.

4.4. Treatment with AZA (in both phase I and phase II) may be repeated every 28 days. The start of subsequent cycles may be delayed to allow for recovery of any adverse events to grade 1 or less.

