5.2. Evaluation During Study

- 5.2.1. Physical exam and evaluation of toxicity (clinic visit or telephone interview):
 - 5.2.1.1. Phase I portion: every 2 weeks for the first month, then every month for the first 3 months, then every 3 months (± 1 month) until month 6, then every 6 to 12 months.
 - 5.2.1.2. Phase 2 portion: every 3 months (± 1 month) until month 6, then every 6 to 12 months.
- 5.2.2. CBC, platelet, differential every 1-2 weeks for 8 weeks, then at the start of every cycle. Differential not required if $WBC \leq 0.5 \times 10^9/L$.
- 5.2.3. Bone marrow aspirate with cytogenetics or FISH every 3-6 months in year 1, then as clinically indicated.
- 5.2.4. Total bilirubin, SGPT or SGOT, and creatinine every 1-2 weeks for 8 weeks, then before each cycle.
- 5.2.5. Quantitative PCR (peripheral blood and/or bone marrow) before each cycle for 3 cycles, then every 3-6 cycles until one year, then every 6-12 cycles.
- 5.2.6. Peripheral blood and bone marrow for correlative studies every 3-6 months in year 1, then every 6-12 months. Methylation studies will also be done on days 5, 10 and 28 (all ± 3 days) of the first cycle. Not all optional samples may be collected. (Optional – Appendix A, B & C).

6. Criteria for Response

- 6.1. A favorable response for the primary endpoint is defined as a greater than a one-log reduction of BCR-ABL transcript levels from the baseline level at the time vaccination was initiated, or a disappearance of BCR-ABL transcripts (i.e., complete molecular response).

7. Criteria for Removal from Study

- 7.1. The patient receives CML-directed therapy other than TKI and AZA.
- 7.2. The patient develops disease progression defined as confirmed loss of CCyR, confirmed loss of CHR or transformation to accelerated or blast phase.
- 7.3. The dose of TKI is increased or new therapies for their leukemia are added.
- 7.4. The patient has a continuous interruption of imatinib therapy for greater than 6 weeks.
- 7.5. The patient withdraws consent.
- 7.6. The treating physician considers it in the best interest of the patient.
- 7.7. Pregnancy or suspected pregnancy

8. Adverse Event Reporting

- 8.1. Adverse event is any untoward medical occurrence that may present during treatment with a pharmaceutical product but which does not necessarily have a causal relationship with this treatment.

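### Phase I replaces any DLT-free patient who leaves before four weeks, whatever the reason, so toxicity-driven exits fall out of the 3+3 count and can bias the MTD upward

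*Combined protocol and SAP*

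**What the plan says.** The replacement rule stands in section 4.2.1: "Patients who come off study prior to the first four weeks and have not experienced a DLT will be replaced". It has two conditions, early exit and no DLT. The sentence before it sets the observation period: "All patients treated at any one dose level must have been observed for at least four weeks before escalating to the next dose level". Section 9.2.1, which restates the 3+3 algorithm, adds nothing on replacement or evaluability. Section 9.2.2 defines the MTD by the number of patients treated at a level.

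Section 4.2.3.1 sets the DLT window: "DLT will be defined by events that are clinically significant and possibly related to study drug occurring during the first 4 weeks (1 cycle) of" […]. Some events qualify as soon as they are graded and attributed. Section 4.2.3.2 begins "Non-hematologic DLT is defined as grade 3 or 4 toxicity (NCI common criteria, version 4.0) that is clinically significant and" and then requires at least a possible relation to study drug. Others qualify only after a further step: "Grade 3 or 4 nausea, vomiting and diarrhea will be considered DLT only if not controlled by optimal therapy". Under 4.2.3.3, most grade 3 biochemical changes need clinical consequences, and electrolyte changes must fail correction.

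Section 7 has no removal criterion for toxicity as such. Exits for that reason would come under withdrawal of consent (7.5) or under 7.6: "The treating physician considers it in the best interest of the patient".

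**The concern.** The phase I primary objective (1.1.1) is to establish the DLT and MTD of the combination. The count that decides this should describe patients treated at a level. Under 4.2.1 it describes patients who either had a DLT or remained on study for four weeks. Someone who leaves in week 2 while gastrointestinal toxicity is still being treated, or with an electrolyte disturbance still being corrected, has no DLT at that moment and is replaced by someone else. If the reason for leaving is related to the outcome being counted, the exclusion is informative.

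Each decision rests on three or six patients, so one such exclusion can change it. The result decides whether 75 mg/m² for 3 days or a lower level goes into phase II, where 36 − 6 = 30 further patients are enrolled. Replaced patients may also be hard to see afterwards. Section 8.2 puts only unexpected adverse events on the case report form and lists myelosuppression and fatigue as expected.

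**Working it through.** **The plan's own figures.** Section 9.2 lists three levels. With up to six patients each, 3 × 6 = 18, the stated phase I maximum. The total is 18 + 36 − 6 = 48, as in 9.1. Both reproduce, and neither is disputed. The plan gives no operating characteristics for the 3+3 and no early-exit rate, so all rates below are assumptions.

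**Clearing a level.** From 4.2.2 and 9.2.1, a level is cleared with 0/3, or with 1/3 followed by 0/3. If r is the DLT probability per counted patient:

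P(clear) = (1 − r)³ + 3r(1 − r)⁵

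**Illustration 1: only would-be DLT patients leave.** Let p be the true DLT rate and f the share of would-be DLT patients who leave before the event qualifies and are replaced. Then r = p(1 − f)/(1 − pf). At p = 0.33:

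| f | r | P(clear) |
|---|---|---|
| 0 | 0.330 | 0.434 |
| 0.25 | 0.2475/0.9175 = 0.270 | 0.557 |
| 0.50 | 0.165/0.835 = 0.198 | 0.714 |

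**Illustration 2: other patients leave too.** If a share g of patients who would not have had a DLT also leaves, r = p(1 − f)/(1 − pf − (1 − p)g). With p = 0.33, f = 0.25 and g = 0.10, r = 0.2475/(1 − 0.0825 − 0.067) = 0.2475/0.8505 = 0.291. That is about 12% below 0.33, against 18% below when g = 0. P(clear) = 0.709³ + 3 × 0.291 × 0.709⁵ = 0.356 + 0.156 = 0.51. With g = f, r = p and there is no bias.

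**When the direction is upward.** Let d be the rate of completed DLTs, w the share who leave early for toxicity without a DLT, and q the DLT risk those leavers would have had if they had stayed. Replacement makes the counted rate d/(1 − w). Had they stayed, it would be d + wq. Replacement understates the rate only when q > d/(1 − w). For d = 0.20 and w = 0.10 the break-even is 0.20/0.90 = 0.222, and P(clear) under replacement is 0.660. Had the leavers stayed:

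- q = 1: rate 0.30, P(clear) 0.494
- q = 0.5: rate 0.25, P(clear) 0.600
- q = 0.20: rate 0.22, P(clear) 0.665
- q = 0: rate 0.20, P(clear) 0.709

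Replacement is therefore too permissive in the first two cases, about neutral in the third and slightly conservative in the last.

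**The case against.** A reader might infer that the MTD is certain to be biased upward and that every error favours escalation. The documents do not support that. They give no exit rate and no evidence about the leavers' risk, and the break-even shows that the direction depends on that risk. Illustration 1 also builds in its result by letting only future DLT patients leave.

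The route is narrow as well. A clinically significant, possibly related grade 3–4 non-hematologic event that meets 4.2.3.2 is already a DLT, and that patient stays counted after leaving. Dosing at the 9.2 levels lasts 3 days per cycle. Sections 4.4 and 4.5.1 respond to toxicity with a delay or a temporary stop, which is not exit from the study. There are also safeguards. SAEs are captured to 30 days after the last dose unless consent is withdrawn (8.4). All dosed patients enter the toxicity analysis (9.4). Phase II has continuous DLT monitoring (9.3.2), and its starting dose is capped at 75 mg/m² for 3 days.

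These points limit the size of the problem and rule out a claim of certain bias. They do not close the gap. Sections 4.4 and 4.5.1 do not prevent exit under 7.5 or 7.6. Section 9.4 is not stated to govern escalation. SAE capture does not say how a later event enters the 3+3 count, and a DLT need not be serious. Phase II monitoring comes after the dose is chosen and uses the same DLT definition. The cap does not settle whether 75 mg/m² for 3 days or a lower level should go forward, which is the decision at issue.

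A reader might also add cytopenia to this point, because hematologic DLT must be "lasting for 6 weeks or more after the start of a course" (8 weeks with a normocellular marrow). That criterion cannot be complete at week four for a patient who stays either. It is a separate conflict with the four-week window, and those passages must be reconciled in their own right.

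**Conclusion.** The concern holds in conditional form. As written, 4.2.1 permits exclusion from the 3+3 count for reasons related to the outcome, and no other section restores those patients to it. This can lower the apparent DLT rate and raise the MTD when toxicity-driven leavers have a DLT risk above d/(1 − w), which is 0.22 at d = 0.20 and w = 0.10. That is plausible for patients who leave because of a developing toxicity, but the documents do not show it.

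The size is unknown. The rise from 43% to 56% in clearing a level with a true DLT rate of 33% assumes that 25% of would-be DLT patients leave first and nobody else does. It falls to 51% if 10% of the other patients also leave, and to no rise if both groups leave at the same rate. These figures show sensitivity and are not estimates for this trial. A change is still justified, because the decision rests on three or six patients and the remedy is cheap.

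**What to change.** Amend 4.2.1, and repeat the rule in 9.2.1:

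- Replace only patients with no DLT whose exit before four weeks is documented as unrelated to study treatment.
- Do not replace patients who leave mainly because of possibly drug-related toxicity. Keep them in the 3+3 denominator and follow them for DLT through the four-week window where consent allows. The existing SAE capture makes this practicable.
- If the outcome of such an exit cannot be established, do not treat the patient as DLT-free. State in advance a conservative rule for the escalation decision only, such as documented adjudication against 4.2.3 before escalating, and show the decision with that patient counted as a DLT.
- Report all replaced patients with the reason and any toxicity at exit.

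Automatically counting as a DLT every leaver for whom toxicity played some part would overcorrect. It could turn a low-grade event into a DLT against 4.2.3. At d = 0.20 and w = 0.10 it would cut clearance to 0.494, when the figure would be 0.665 if the leavers' true risk were 0.20.

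The cost is a few sentences and a recorded reason for each early exit. No larger sample is needed, and there should be slightly fewer replacements. The small downside is that an occasional patient with tolerable toxicity may count against a level.

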4.2.3. Definition of Dose-Limiting Toxicity (DLT)

4.2.3.1. DLT will be defined by events that are clinically significant and possibly related to study drug occurring during the first 4 weeks (1 cycle) of therapy.

4.2.3.2. Non-hematologic DLT is defined as grade 3 or 4 toxicity (NCI common criteria, version 4.0) that is clinically significant and

considered to be at least possibly related to the study drug. Grade 3 or 4 nausea, vomiting and diarrhea will be considered DLT only if not controlled by optimal therapy.

4.2.3.3. Grade 3 biochemical abnormalities (e.g., lipase or bilirubin elevation) will only be considered DLT if accompanied by clinical consequences. Grade 3 or 4 electrolyte abnormalities will only be considered DLT if possibly related to study drug and not corrected by optimal replacement therapy.

4.2.3.4. Hematologic DLT is defined as grade ≥ 3 neutropenia and/or thrombocytopenia with a hypocellular bone marrow lasting for 6 weeks or more after the start of a course. (In case of a normocellular bone marrow, 8 weeks with pancytopenia will be considered DLT). Anemia will not be considered for the definition of DLT.

4.2.4. If dose-level 0 exceeds MTD, subsequent patients will be treated at dose level -1. Additional cohorts at lower doses (down to dose level -4) may be included if higher doses exceed MTD. If dose level -4 exceeds MTD, the study will be terminated.

4.3. **Phase II:** The dose to be used for the phase II portion of the study is $75\text{mg}/\text{m}^2$ daily for 3 days, unless MTD is defined at a lower dose level in the phase I portion of the study in which case that would become the dose to be used for the phase II portion. Other dose levels shown in Table 1 will be used for dose adjustments for toxicity or lack of improvement (as described in section 4.5.5) during therapy. For phase II portion of the study, if at any time patients need to be escalated to dose level +2 or +3, if at any time 33% or more of patients experience DLT at this dose level during the first cycle they receive at this dose, this would be considered to have exceeded MTD and that dose level should not be used any further.

4.4. Treatment with AZA (in both phase I and phase II) may be repeated every 28 days. The start of subsequent cycles may be delayed to allow for recovery of any adverse events to grade 1 or less.

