9.2. Phase I

The primary objective of phase I part is to determine the maximum tolerated dose (MTD) of AZA; and the primary endpoint is the occurrence of dose-limiting toxicity (DLT: section 4.3.3) within the first course of treatment. Standard 3+3 design will be used. The starting dose is 50 mg/m²/d x 3 days (Table 1).

Dose level	AZA (mg/m ² /d x 3 days)
-1	25
0	50
1	75

9.2.1. The 3+3 algorithm is described below:

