9.2.1.1. Three patients will be enrolled at the starting dose level

9.2.1.2. If 0/3 patient experiences DLT at a given level, enroll three patients to the next higher dose level

9.2.1.3. If 1/3 patient experiences DLT at a given level, enroll additional three patients to the same dose level

9.2.1.4. If 2/3 or 2/6 patients experience DLT at a given level, the MTD has been exceeded and dose escalation will be stopped. Up to three additional patients will be enrolled at the next lower dose level if only 3 patients were treated at that level.

9.2.2. MTD is defined as the highest dose level in which 6 patients have been treated and one or fewer patient experiences DLT.

The MTD identified in phase I part will be recommended for phase II. If MTD is not determined, the highest AZA level of 75 mg/m²/d x 3 days will be used as the recommended phase II dose.

A maximum of 18 patients will be accrued for phase I part. The data from the 6 patients treated at the recommended phase II dose level (MTD or 75 mg/m²/d x 3 days if MTD is not determined) will be used in phase II part.

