9.3. Phase II

The primary endpoint for phase II portion is the decrease of transcript levels by at least one log (or undetectable transcript level) within 12 months. Including the 6 patients treated at the recommended phase II dose level in the phase I part, a total of 36 patients will be accrued.

9.3.1. **Efficacy Monitoring**

Since the efficacy of the drug will be assessed over a long period of time (12 months) and the accrual rate is relatively fast (1-2 patients per month), no formal futility monitoring rule will be applied. However, the PI and the study committee will meet regularly, and the study will be stopped early if consensus has been reached on any clear indications of poor efficacy of the drug.

9.3.2. **Toxicity Monitoring**

The method of Thall, Simon, and Estey will be used to perform interim safety monitoring [1]. The safety monitoring of the trial will be initiated after the first 6 patients have been evaluated, and then monitored continuously. The monitoring rule for toxicity is $P(\theta_E > 0.20 | \text{data}) > 0.90$, where θ_E is the proportion of any DLT (as defined in section 4.3.3), and is assumed to follow a non-informative prior of Beta (0.4, 1.6). Namely, the trial will be terminated if at any time during the study there is a more than 90% chance that the average rate of DLT is more than 20%. The stopping boundaries of the trial are ≥ 3 out of 6, ≥ 4 out of 7, ≥ 5 out of 10, ≥ 6 out of 14, ≥ 7 out of 18, ≥ 8 out of 22, ≥ 9 out of 26, ≥ 10 out of 30, ≥ 11 out of 34 patients experienced DLT.

Table 2: Operating characteristics of Safety Monitoring (based on 10000 simulations)				
True Probability	Stop Probability	Trial Sample Size Percentile		
		25%	50%	75%
0.10	0.02	36	36	36
0.20	0.25	36	36	36
0.30	0.69	6	17	36
0.40	0.96	6	8	16

All calculations were performed using Multc99.

9.4. **Statistical Methods**

Data analysis will be performed using SAS or S-plus, whichever is appropriate. All patients who receive at least one dose of therapy will be included in the primary efficacy and toxicity analysis. Patients who do not have molecular response and

withdraw within 12-months after initiation of treatment will be counted as failure in the primary efficacy analysis.

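### Escalation may be decided at week 4, but a haematologic DLT cannot be established before week 6 or 8, and no rule holds the cohort decision for an unresolved cytopenia

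*Combined protocol and SAP*

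**What the plan says.** Section 4.2.3.1 defines DLT through "events that are clinically significant and possibly related to study drug occurring during the first 4 weeks (1 cycle) of therapy". Section 4.2.1 says that all patients at a level "must have been observed for at least four weeks before escalating to the next dose level". Section 9.2 makes DLT "within the first course of treatment" the phase I primary endpoint, and 9.2.1.2 escalates on 0/3 with no further condition.

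Section 4.2.3.4 defines haematologic DLT as grade 3 or worse neutropenia and/or thrombocytopenia "with a hypocellular bone marrow lasting for 6 weeks or more after the start of a course". For a normocellular marrow, "8 weeks with pancytopenia will be considered DLT".

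Three other provisions bear on the gap:

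- Section 4.4 concerns the individual patient: "The start of subsequent cycles may be delayed to allow for recovery of any adverse events to grade 1 or less".
- Section 4.5.4.4 holds AZA for low counts, again patient by patient.
- Section 5.2.2 schedules blood counts every 1 to 2 weeks for 8 weeks, without linking them to the cohort decision.

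Section 9.2.2 defines the MTD as the "highest dose level in which 6 patients have been treated and one or fewer patient experiences DLT". Phase II safety monitoring under 9.3.2 "will be initiated after the first 6 patients have been evaluated, and then monitored continuously".

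**The concern.** Read literally, the two parts of the DLT definition conflict, because a 6-week duration cannot be completed inside a 4-week window. The sensible reading is onset in cycle 1 with confirmation at week 6 or 8. The 8-week count schedule fits that reading, but it is not written down. Even on that reading the event cannot be classified at the earliest time the plan allows escalation.

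At stake is the phase I primary endpoint. It decides the single upward step in 9.2 (50 to 75 mg/m² for 3 days) and whether 75 mg/m² becomes the phase II dose. The error runs in one direction: a patient whose cytopenia is later confirmed as a DLT may be scored as having none when the decision is taken, so a too-toxic level is less likely to be recognised. Myelosuppression is also a foreseeable toxicity, since section 2.4 lists bone marrow among the main target organs of azacitidine. In addition, 4.2.1 replaces only patients who leave before week 4. A patient who leaves at week 5 with unresolved cytopenia is not replaced, and no rule says how to score that patient.

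**Working it through.** **The plan's own figures.** The plan gives no number for this point. The figures that use the DLT definition reproduce and are not in dispute. With the Beta(0.4, 1.6) prior, all nine stopping boundaries in 9.3.2 match. Exact stop probabilities are 0.025, 0.256, 0.707 and 0.954, against 0.02, 0.25, 0.69 and 0.96 in Table 2.

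**Timing.** The earliest decision is day 28 of the last patient (4.2.1). The earliest haematologic DLT is day 42 or day 56 (4.2.3.4). The open window is 42 − 28 = 14 days, or 56 − 28 = 28 days.

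Section 9.1 gives accrual of 1 to 2 patients a month. With even spacing and 30.4-day months, when the last patient reaches day 28 the patient before is at:

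- 1 a month: 28 + 30.4 = day 58.4, past both criteria;
- 2 a month: 28 + 15.2 = day 43.2, past the 6-week criterion but not the 8-week one.

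So usually only the last patient is open.

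**Effect on the decision.** Let h and n be the haematologic and non-haematologic DLT rates. They are assumptions, taken as independent, since the documents give none. The combined rate is c = 1 − (1 − h)(1 − n). The calculation assumes that the team decides at 4 weeks, scores the open last patient on non-haematologic DLT only, and escalates at 0/3. An open patient in a first cohort is taken as resolved by the time a second cohort at that level is decided.

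*3+3, everything visible:* P(MTD exceeded) = P(≥2 of 3) + P(1 of 3) × [1 − (1 − c)³].

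*3+3, last patient open:* with v = 1 − (1 − c)²(1 − n),

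P = c² + 2c(1 − c)n + 2c(1 − c)(1 − n)[h + (1 − h)v] + (1 − c)²n·v.

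*Six-patient decision (≥2 of 6):* six patients at rate c, against five at c and one at n.

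Worked case, h = n = 0.10:

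- c = 1 − 0.9 × 0.9 = 0.19.
- 3+3 full: 0.0946 + 0.3740 × 0.4686 = 0.270.
- 3+3 open: v = 1 − 0.6561 × 0.9 = 0.4095. The four terms are 0.0361 + 0.0308 + 0.1298 + 0.0269 = 0.224.
- Six full: 1 − 0.81⁶ − 6 × 0.19 × 0.81⁵ = 1 − 0.2824 − 0.3975 = 0.320.
- Six open: 1 − 0.3138 − 0.4029 = 0.283.

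Probability of declaring the MTD exceeded (gaps from unrounded values):

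| h / n | 3+3 full | 3+3 open | gap | six full | six open | gap |
|---|---|---|---|---|---|---|
| 2% / 10% | 0.125 | 0.117 | 0.008 | 0.151 | 0.145 | 0.006 |
| 5% / 10% | 0.176 | 0.155 | 0.022 | 0.212 | 0.194 | 0.017 |
| 10% / 10% | 0.270 | 0.224 | 0.046 | 0.320 | 0.283 | 0.037 |
| 20% / 10% | 0.464 | 0.374 | 0.090 | 0.536 | 0.468 | 0.068 |
| 30% / 5% | 0.575 | 0.446 | 0.129 | 0.652 | 0.559 | 0.093 |

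**Exposure during the window.** Enrolments while the status is open range from 14/30.4 × 1 = 0.46 to 28/30.4 × 2 = 1.84. This applies to entry at the next dose level and equally to the lag in the 9.3.2 rule.

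**The case against.** The strongest reply is that the loss is provisional. The four weeks are a minimum, counts are taken to week 8, and a team looking at a grade 3 cytopenia at week 4 would be expected to wait. Section 9.2.2 has no day-28 data cut, and the first course in 9.2 is not fixed at 28 days, so a week-6 confirmation might still update the tally. The event is also demanding, and no passage supports haematologic DLT rates of 20 to 30%. In 9.3.2 a pending patient can be read as not yet evaluated. Finally, the 6- or 8-week branch needs a marrow, while 5.2.3 schedules marrows only every 3 to 6 months.

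Much of this stands as a limit on size. A team that waits has no gap, the larger gaps lack support, and the phase II rule is only delayed. The conflict remains, though. Waiting is left to discretion, and the literal 4-week limit in 4.2.3.1 would exclude the late event that is supposed to correct the tally. Phase II monitoring is not a full substitute: a corrected 2 of 6 means the MTD is exceeded in phase I but does not reach the 9.3.2 boundary of 3 of 6. Marrow cellularity is already required by 4.2.3.4, so that need does not arise from the fix.

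**Conclusion.** The concern holds. As written, the rules allow a cohort to be scored 0/3 or 1/6 while its last patient's haematologic DLT status cannot yet be known, and the literal 4-week window would exclude the event once it is confirmed.

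The effect is modest. The probability of declaring the MTD exceeded falls by less than 0.01 at an assumed 2% haematologic rate, by about 0.02 at 5%, and by 0.04 to 0.05 at 10%, each with 10% non-haematologic DLT. Losses of 0.07 to 0.13 need haematologic rates of 20 to 30%, which nothing in the documents supports. All of these rest on assumed, independent rates, evenly spaced accrual, a decision at the 4-week minimum, and the open patient being scored as having no DLT. The conflict in the text depends on none of these assumptions. The plan should be corrected because the error always favours escalation and the remedy is cheap. The stopping boundaries, sample size and power are unaffected.

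**What to change.** - **4.2.3.1:** state that cytopenia starting in the first cycle at a dose and meeting the 4.2.3.4 criterion at week 6 or 8 is a DLT. Use matching wording in 9.2 and 4.3.
- **4.2.1:** a patient with unresolved grade 3 or worse neutropenia or thrombocytopenia at week 4 is not counted as free of DLT. Escalation or the MTD decision waits until counts recover or the 6- or 8-week criterion has been assessed.
- **9.3.2:** treat such a patient as not yet evaluated.

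The cost is protocol wording plus a delay of at most 2 to 4 weeks per cohort, and only when such a cytopenia persists at week 4. Other cohorts still decide at day 28. In phase I the blood counts needed are already scheduled to week 8 (5.2.2). The total of 48 patients, the 36 in phase II and the 87% power do not change.
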